### (vi) Evaluation plan

#### 1. Outcome evaluation

Obesity-related indicators: obesity-related indicators include changes in BMI ( $\text{kg/m}^2$ , measured weight in kilograms divided by measured height in meters squared), waist circumference in centimeters, waist-to-height ratio (%), and % body fat. In addition, changes in body weight categories (such as changes from overweight/obesity to normal weight, changes from obesity to overweight or vice versa) will also be recorded, where the classification criteria using age- and gender-specific BMI cut-off points suggested by Cole will be adopted (Cole 2000).

Height will be measured to the nearest 0.1 cm using a stadiometer (Holtain Ltd., Pembrokeshire, United Kingdom). Weight will be measured to the nearest 0.1 kg on a digital balance scale (Seca, max. 200 kg, Germany) with the subject wearing lightweight clothing and no shoes. Then BMI will be calculated from weight and height. The waist circumference (in cm) will be measured midway between the lowest rib margin and the top of the iliac crest at the end of gentle expiration. The measure will be performed with a flexible meter ribbon accurate to 0.1 cm. The % body fat will be assessed by bio-impedance (Body stat 1500 MDD, Douglas, Isle of Man, United Kingdom).

All obesity-related indicators will be measured at the T1 (pre-intervention), T2 (end of Stage 1), T3 (end of Stage 2), and T4 (post-intervention) among all participants in the two groups.

***Heart rate measurements:*** HRrest of each participant will be measured at the beginning of each stage using the standard procedure. Participants will wear a Polar T31 Heart Rate Monitor (Polar Electro Inc., Lake Success, NY, USA) during HRrest measurement; their values will be averaged over the 20-min collection period. Exercise HR of each participant will be monitored using the Polar T31 during the instructional process following the standard procedure.

## 2. Process assessment

For the target schools, all participants' parents will be given a self-administered questionnaire right after the major intervention. The questionnaire will aim at evaluating if the participants can get the impacts of the intervention, think the intervention is interesting and useful for preventing their children from obesity, and so forth. In addition, the PE teachers involved will be surveyed and asked about their opinions about the PA intervention (e.g., satisfaction, perceived usefulness and acceptability, etc.). A report summarizing our experiences will be prepared as deliverables for the participating schools and other local schools.

### (vii) Results analysis

IBM SPSS Statistics 23 will be used for data analysis. Continuous variables (e.g., BMI) will be presented with mean (standard deviation, SD) and/or median (interquartile rage, IQR) values. All continuous variables pre-intervention will be tested for between-group differences using independent sample t-test. Normality will be checked by QQ-plots, and tested for equal variance assessed by Levene's test. If skewed, the data will be logarithmically transformed before applying t-test.

A general linear model two-way repeated measure ANCOVA will be used to compare significant differences in the changes in the continuous outcome variables between the two groups, where group and time are the two factors of interest (Elmahgoub, 2011). Variables will be selected in a stepwise manner and only those with  $p < 0.1$  kept in the final models. A significance level of 0.05 will be adopted (two-tailed test). Intention-to-treat analysis will be adopted and performed to avoid bias from withdrawals or protocol deviations.

[Word Count: 2788 ]

(e) Existing Facilities:

We have all facilities needed in this project, including stadiometers, digital balance scales, Body stat 1500 MDD, Polar T31, ActiGraph accelerometers, questionnaires of subjective measurements of PA and eating habits.

This project will be undertaken by staff in Department of Physical Education, Hong Kong Baptist University (DPE) and JC School of Public Health and Primary Care, Chinese University of Hong Kong (SPHPC). The DPE has a long and proud history of its outstanding achievements across an array of academic fields related to physical education, sport and leisure services, whilst the SPHPC is made up of diverse professionals, such as health promotion specialists, epidemiologists, public health experts, and clinicians. Both of the two institutions will fully support this project. In addition, the team members from the both universities have been smoothly and successfully collaborating with each other on several studies in the past years. Last but not the least, The DPE holds two undergraduate programmes (AD and Top-up) with a focus on special population, through which it keeps a very close relationship with local special schools. Many schools receive our current students to fulfil their internship courses. A large portion of PE teachers are our alumnus. Taking our previous study as an example, we successfully invited more than one third of all special schools for children with mild and moderate ID into that study. Of the participating schools, three proactively asked if we could provide intervention programmes to them in future. Most schools gave positive answers when we asked the possibility to implement an intervention in their schools.

(f) Justification of Resource Requirements:

(i) Details

1. Research Assistant: A full-time project coordinator is needed to coordinate the data collection, implement the intervention, and assist in data analysis. A total cost of HK\$ 268200 was estimated according to our university's pay structure (HK\$14900/months for 18 months).
2. Payment to student helpers: we will need 4 student helpers in outcome measurements (height, weight, waist circumference, waist-to-height ratio, and % body fat) and implementation of the intervention. The hourly payment rate is HK\$49/hour, each student will work 10 months (at a rate of 1 hour/session, 2 sessions/week, and 4 weeks/months, totally 80 hours/student helper), generating a total cost of HK\$ 15680.
3. Incentives for participants: in order to increase the participation rate and decrease the attrition rate, a token incentive of a HK\$100 coupon (e.g. supermarket coupon) will be given to the participants competing the whole study. Thus, a total cost of HK\$6400 was estimated. In addition, rewards (e.g. stickers) will be given to the participants who complete each intervention session (a total of 72 sessions). A total of HK\$2000 was then estimated. Governance system: We will purchase coupons and stickers via the Finance Office (FO) of our university. We will ask a parent/guardian of each participant sign on the record sheet for receiving a coupon of HK\$100. The FO will monitor the disbursement of incentives to ensure accountability and traceability.
4. Conference: we will present our findings on at least an international conference. A total cost of HK\$10000 was then estimated.
5. Publication costs: We will publish at least one article in an international

peer-reviewed journal. We want it to be open access and freely available online. Open access publishing is a charged service. For example, a quality journal levies an article-processing charge of USD2785 (around HKD 21723) for each article accepted for publication. A total cost of HK\$20000 was then estimated.

6. Transportation cost: the research staff will travel between schools and office to implement the intervention. A total cost of HKD 8640 was estimated, at a rate of HKD30/travel, 72 travels/person, and 4 persons).

(ii) Estimated revenue or recurrent income (if any) to offset the expenditure of the project  
Nil

(iii) Supplementary sponsorship (monetary or non-monetary) (if any) to cover any expenditure or resource requirement of the project  
Nil

(g) Purpose and Potential:

(i) How will this project enhance your community's capacity to promote health in the long run  
We expected that our programme, if effective, would be welcomed and adopted by other special schools to reduce obesity among their students in the future. We hold close collaborative relationship with many special schools, we have many alumnus working in the special schools, and we therefore could promote our programme via those links if it is effective. In addition, the effective model can also be extended to reach students with ID in normal schools. We will disseminate our findings by presenting on international conferences, publishing journal articles, and building up online platforms for learning and sharing to achieve as large benefits as possible. In the long run, we will equip our undergraduates with the effective APA programme, which they will bring to their receiving schools during internship and to their working schools after graduation.

(ii) How the project can be sustained after the funding period  
The APA programme will be designed and implemented by researchers and PE teachers together. If it is effective, the participating schools can independently run the APA programme after the funding period. Upon the completion of the project, we will building up and maintain online platforms via Facebook/Instagram with all deliverables generated from the project. The platforms can be accessed for free by teachers, parents, and other publics to learn and share experiences in obesity interventions. In addition, we will integrate the programme into our courses. Thus, our students can continue delivering the APA programme in the long run.

(h) Key References:

Commission on Youth, Hong Kong. (2014). Youth in Hong Kong: A Statistical Profile 2012. (Data is accessible on May 13, 2016 on <http://www.coy.gov.hk/en/research/index.html> ).

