## 2. Description of control:

The participants in the control group will receive routine PE classes as usual during the intervention period (in the academic year of 2018/19).

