### (iii) Contingency / alternative plan if any problem encountered during implementation

During the intervention, any participant, no matter in which group (intervention or control), will be asked to suspend or even cease participation if being proved not to be suitable for the study any more due to any reason. For instance, if a participant is caught by a bad cold, his/her situation will be evaluated by both researchers and teachers on spot. Sh/e will be asked to keep the original plan, undertake some low-intensity activities, or skip the planned PA session, according to evaluation results. In addition, the case will be recorded and considered in data analysis and result interpretation later on. For a participant with an attendance rate below than 80%, his/her data will be excluded from data analysis. An attrition rate of 20% was therefore involved in sample size estimation to ensure a sufficient power for data analysis. In addition, intention-to-treat analysis will also be performed to avoid bias from the withdrawals.

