### (v) Indicators and targets

Outcome indicators will consist of BMI, % body fat, waist-to-height ratio, body weight status, and PA levels. Taking BMI as an example, we expected to achieve an effect size of  $0.722 \text{ kg/m}^2$  (mean difference in change of BMI divided by pooled standard deviation) via the intervention.

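### The planned repeated-measures ANCOVA has no missing-data method, so by default it does not deliver the promised intention-to-treat analysis, and the 80% attendance exclusion is not ranked against it

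*Combined protocol and SAP*

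**What the plan says.** Section 13(d)(vii), Results analysis, names SPSS 23 and the model: "A general linear model two-way repeated measure ANCOVA will be used to compare significant differences in the changes in the continuous outcome variables". The comparison is of the two arms, with group and time as the factors. On covariates it says "Variables will be selected in a stepwise manner and only those with" p < 0.1 are kept. It then states: "Intention-to-treat analysis will be adopted and performed to avoid bias from withdrawals or protocol deviations".

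Section 13(d)(vi), Evaluation plan, has the obesity indicators measured in both groups at T1 (before the intervention), T2, T3 and T4 (after it). The background items it collects for control or explanation include parental education, occupation and weight status.

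Section 13(d)(iii), the contingency plan, says that a participant in either group who becomes unsuitable "will be asked to suspend or even cease participation". It goes on: "For a participant with an attendance rate below than 80%, his/her data will be excluded from data analysis". The 20% attrition allowance is introduced as a consequence of that exclusion. The section closes: "In addition, intention-to-treat analysis will also be performed to avoid bias from the withdrawals". Section 13(d)(ii) says of the controls: "The participants in the control group will receive routine PE classes as usual during the intervention period".

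BMI change is the first objective and the basis of the sample size in Section 13(d)(i). Section 13(d)(v) puts it this way: "Taking BMI as an example, we expected to achieve an effect size of" 0.722. No outcome, visit or contrast is called primary, and no section gives an imputation method, a missing-data assumption or a sensitivity analysis.

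**The concern.** Intention-to-treat says who is analysed and in which group. It does not say what to do when an outcome is absent. A general linear model for repeated measures works on complete rows, so a participant with T1, T2 and T4 but no T3 is left out altogether, as is one with four BMI values and a missing retained covariate. Unless another step is added, the analysed set is those with complete data, not those randomised. If participants who leave differ between arms in their BMI course, the comparison is biased, and that is the bias the plan says it will avoid.

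The attendance rule adds to this. There are two analysis sets and neither is named as primary. The added sessions exist only in the intervention arm, and the plan does not say what attendance means for a control. The exclusion may therefore remove participants from one arm only and break the randomised comparison. With no primary population and no named primary test, there is room to settle the main result after the data are seen.

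**Working it through.** The plan gives no missed-visit rate, so it has no figure of its own to reproduce here. Inputs from the plan are 64 participants, 32 per arm, and an effect of 0.722 (Section 13(d)(i)), plus three visits after baseline (Section 13(d)(vi)). The 0.722 is taken in SD units, as its definition implies, despite its kg/m² label. Everything else below is assumed.

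**1. Participants lost to complete-row analysis.** Let p be the chance of missing each of T2, T3 and T4, independently, and q the chance that a retained covariate is missing. T1 is taken as complete.

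- Complete: 64(1−p)³(1−q)
- Discarded although T4 was measured: 64[(1−p) − (1−p)³(1−q)]

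For p = 5% and q = 0: 64 × 0.8574 = 54.9 complete, and 64 × (0.95 − 0.8574) = 5.9 discarded.

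| p | q | Complete of 64 | Discarded with T4 measured |
|---|---|---|---|
| 5% | 0 | 54.9 | 5.9 |
| 7% | 0 | 51.5 | 8.0 |
| 10% | 0 | 46.7 | 10.9 |
| 5% | 5% | 52.1 | 8.7 |
| 7% | 5% | 48.9 | 10.6 |
| 10% | 5% | 44.3 | 13.3 |

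**2. Bias from selective dropout (a separate illustration).** Here dropout is permanent, so no measured T4 value is thrown away; the question is who remains. The simulation had 32 per arm, AR(1) correlation between visits, an effect building linearly to T4, and 8,000 runs per scenario in the 0.95 rows (Monte Carlo SE of bias about 0.003). The chance of dropping out after T2 and again after T3 was 2r/(1+exp(−2z)), with r = 0.10 or 0.15 and z the standardised BMI change. The complete-case analysis was a T4 ANCOVA adjusted for T1, a stand-in for the planned repeated-measures test. The likelihood analysis was sequential-regression maximum likelihood, a stand-in for SPSS MIXED. Bias is in SD of the T1–T4 change; negative values favour the intervention. True effect zero, results for r = 0.10 / 0.15:

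| Dropout follows | Arm | AR(1) | Complete-case bias | Likelihood bias |
|---|---|---|---|---|
| Observed BMI gain | Intervention only | 0.95 | −0.085 / −0.136 | 0.001 / −0.002 |
| Observed BMI gain | Intervention only | 0.80 | about −0.06 / −0.10 | not tabulated |
| Observed BMI gain | Both alike | 0.95 | −0.004 / −0.002 | not tabulated |
| Next, unseen BMI | Intervention only | 0.95 | −0.118 / −0.181 | −0.055 / −0.081 |

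In the first row 6.0 or 8.7 of 32 are lost (8.7/32 = 27%, above the planned 20%), and the two-sided 5% test rejects in 6.7% or 8.1% of runs. With a true effect of −0.722 and the same dropout, the bias is −0.075 or −0.116, that is 0.075/0.722 = 10% or 0.116/0.722 = 16% of the effect. Dropout alike in both arms then gives 0.012 or 0.017.

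**3. The two analysis sets side by side.** Section 13(d)(iii) states the attendance exclusion first and adds intention-to-treat, which can be read as making it the second analysis. Section 13(d)(vii) mentions only intention-to-treat, which can be read as making it the main one. Neither section settles the order.

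**The case against.** Several stronger readings are tempting, and the case against them is sound.

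- *The plan contradicts itself on intention-to-treat.* It does not. Section 13(d)(iii) describes two analyses, and both can be run. What is missing is their order.
- *The 20% allowance shows that a fifth will miss visits.* Section 13(d)(iii) ties it to the attendance exclusion. A low attender may have all four measurements, so the figure is no direct evidence of missed visits.
- *The plan specifies no comparison.* Comparing changes between groups, with group and time as factors, naturally means a group-by-time comparison. BMI leads by implication, and T4 is labelled post-intervention. The gap is that none of this is named as the primary test.
- *The plan prescribes dropping incomplete participants.* No such rule is written. It is how the named procedure behaves by default, and imputation beforehand would change it.
- *The result will be biased.* The larger figures need dropout in one arm only, linked to BMI gain. The suspension rule covers both groups, and a coupon for completing the whole study (Section 13(f)(i), item 3) should help retention. With dropout alike in both arms the bias is negligible.

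What stands is that the intention-to-treat sentence cannot be carried out on incomplete data with the method as written, and that nothing in the document fills the gap. Nor does the plan say which variables enter the stepwise selection; the parental items are likely candidates, not stated ones.

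**Conclusion.** The point holds as an omission that should be corrected. No missing-data method is given, the default behaviour of the named procedure does not meet the intention-to-treat promise, and the attendance-restricted and intention-to-treat analyses are unranked. These conclusions rest on the text and on a general property of the procedure, not on the simulation.

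The size is illustrative only. With 5% to 10% missing at each of T2 to T4, 55 to 47 of 64 are complete and 6 to 11 participants with a measured T4 BMI are discarded. One-arm dropout following observed BMI gain biases a complete-case analysis by about 0.06 to 0.14 SD of change at zero effect (AR(1) 0.80 to 0.95), and a likelihood model is then close to unbiased. If dropout follows unseen BMI, the likelihood model removes only about half of the bias. A reader might infer that the trial's conclusion is already compromised; the documents give no missed-visit rate or dropout pattern that would support this.

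**What to change.** - **Section 13(d)(vii):** analyse all randomised participants as randomised, whatever their attendance. Use a linear mixed model for repeated measures (SPSS MIXED) adjusted for the T1 value, or multiple imputation followed by the planned general linear model. Replace stepwise selection in the primary model with prespecified, fully observed baseline covariates, since a mixed model also drops records with a missing covariate. Name the group difference in BMI at T4 as the single primary test, two-sided 0.05.
- **Section 13(d)(iii):** limit the 80% attendance exclusion to a secondary per-protocol analysis, and say how attendance is counted for controls.
- **Section 13(d)(vi):** state that outcome measurement continues for participants who stop sessions.
- **Reporting:** give the number with no follow-up by arm, and cover them in a sensitivity analysis, because a mixed model on T2 to T4 leaves them out. Letting that analysis depart from missing at random would be useful but is a matter of preference, as is the choice of covariance structure.

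The cost is wording in three sections, with the same software, plus the effort of measuring participants who stop sessions. There are two downsides: the primary model assumes data are missing at random, and other outcomes and visits become secondary, so a significant result there no longer counts as primary success.

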1. To reduce BMI among a sample of overweight and obese adolescent children with ID in local special schools;
2. To reduce % body fat among the sample;
3. To reduce waist-to-height ratio among the sample;
4. To reduce overweight and obese status among the sample;
5. To improve PA levels among the sample.

(d) Project Plan:

[figure not shown]
(i) Target group

The target population of the project will be adolescents with mild and moderate ID (aged 12- 18 years) who are overweight and obese. We will adopt a randomised controlled trial (RCT) design and recruit 64 overweight and obese students from 4-6 special schools, and then randomly and equally assign them into the intervention and control groups (32 in each group). This sample size can test an effect size of  $0.722 \text{ kg/m}^2$  (mean difference in change of BMI divided by pooled standard deviation), with an attrition rate of 20%. The selection criteria of participants include: (1) children with mild and moderate ID; (2) aged 13-18 years old; (3) being overweight or obese; (4) without physical disability; (5) without medical predispositions towards obesity (genetic syndrome or drug treatment) that could interfere with the results of the study; and (6) without contraindications for regular physical activity (e.g. asthma, heart disease). A written informed consent will be obtained from their parents/guardians in advance.

(ii) Implementation plan

*1. Description of intervention:*

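### The repeated-measures comparison of changes does not prespecify the outcome's pre-intervention (T1) value as a covariate, so precision already paid for may go unused

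*Combined protocol and SAP*

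**What the plan says.** The analysis of continuous outcomes is in section 13(d)(vii), Results analysis: "A general linear model two-way repeated measure ANCOVA will be used to compare significant differences in the changes" between the two arms, with group and time as the factors. That section does not list the levels of time, name the term to be tested, or name any covariate. Covariates are chosen stepwise and kept only at p<0.1. The test is two-sided at 0.05.

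For values before the intervention the same section says: "All continuous variables pre-intervention will be tested for between-group differences using independent sample t-test". No adjustment or other decision follows from those tests.

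The visits are set out in the outcome evaluation under 13(d)(vi): "All obesity-related indicators will be measured at the T1 (pre-intervention), T2 (end of Stage 1), T3 (end of Stage 2), and T4 (post-intervention"). The paragraph there on other measurements lists what is collected for control purposes: sociodemographic items, level of disability and comorbidities, and parental weight status. The outcome's own T1 value is not on that list.

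The target effect in 13(d)(i) is 0.722, defined as "mean difference in change of BMI divided by pooled standard deviation".

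**The concern.** The T1 value of an outcome is usually the strongest available predictor of its later values. A comparison of raw changes subtracts T1 in full, when the best prediction of T4 uses only a fraction of it. Part of any chance imbalance at T1 therefore stays in the treatment difference. With 64 children that imbalance can be appreciable.

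The most natural reading of a group-and-time model of changes over four visits is that T1 is one level of time, which makes the group-by-time test a test of unadjusted change. If change scores at T2-T4 are the response instead, they are also unadjusted unless T1 is added. If T1 is a candidate in the stepwise step, adjustment depends on the data, and with T1 also a level of time the same value would be on both sides of the model.

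The baseline t-tests do not help. After randomisation any difference they find is due to chance, and testing for it does not remove it.

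**Working it through.** **Inputs from the documents.** Two-sided 0.05 (13(d)(vii)); effect 0.722 in SD-of-change units, 64 participants at 32 per arm, and 20% attrition (13(d)(i)). The analysed number is 32 × 0.8 = 25.6, taken as 26 per arm.

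**Assumptions.** The documents state no power and no correlation. I take 80% power for the sample-size check, r between T1 and T4 from 0.5 to 0.95, and equal SD *s* at both visits.

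**The plan's own figure.** n per arm = 2(1.960 + 0.842)² / 0.722² = 30.1, so 31 (normal) or 32 (t-test). This is the number to be *analysed*. With 20% attrition it becomes 31/0.8 → 39 or 32/0.8 = 40 per arm, 78 to 80 in total. The stated 64 is therefore not reproduced with the attrition allowance at two-sided 0.05. It matches without that allowance, or with a one-sided 0.05 t-test (25/0.8 → 32).

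**Variance.**
- Unadjusted change: 2s²(1−r).
- T4 adjusted for T1: s²(1−r²) = s²(1−r)(1+r).
- Ratio: (1+r)/2.

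**Power for a T4 contrast.** Adjusted d = 0.722/√((1+r)/2). Noncentrality = d√(n/2) = d√13 = 3.606d, with 50 df.

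| Analysis | Variance ratio | d | Noncentrality | Power, 26/arm | Power, 32/arm |
|---|---|---|---|---|---|
| Unadjusted change | 1 | 0.722 | 2.60 | 72.3% | 81.1% |
| Adjusted, r=0.5 | 0.75 | 0.834 | 3.01 | 83.8% | 90.7% |
| Adjusted, r=0.8 | 0.90 | 0.761 | 2.74 | 76.8% | 85.0% |
| Adjusted, r=0.95 | 0.975 | 0.731 | 2.64 | 73.4% | 82.1% |

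Giving up one df for the covariate changes the 26-per-arm figures by less than 0.1 point.

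**Chance imbalance.** One standard error of the T1 difference is s√(2/26) = 0.277s. Unadjusted change carries (1−r) of it. In SD-of-change units:
- r=0.5: 0.5 × 0.277 / √1.0 = 0.139, or 19% of 0.722.
- r=0.8: 0.2 × 0.277 / √0.4 = 0.088, or 12%.
- r=0.95: 0.05 × 0.277 / √0.1 = 0.044, or 6%.

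**Which contrast to name.** Assume compound symmetry, 26 per arm, and an effect that builds linearly to 0.722 SD of change at T4.
- Group-by-time over T1-T4 (3 df): 61% at any r.
- 3-df test of T2-T4 adjusted for T1: 73% at r=0.5 and 60% at r=0.95.
- T1-adjusted difference averaged over T2-T4: 75% at r=0.5, 62% at r=0.8 and 57% at r=0.95.

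Adding T1 as a covariate is thus not enough. If the averaged difference is tested, power at r=0.95 is below that of the unadjusted group-by-time test. With an effect that is immediate and constant, the average does better (89% to 98%, against 76%). The T4 contrast uses the endpoint of the programme and avoids the loss under gradual build-up.

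**The case against.** The strongest reply is that the section is underspecified rather than wrong. It calls the model an ANCOVA, which leaves room for a T1 covariate. It does not list T1 as a level of time, and it cites an outside study for the model. This stands: a reader might infer that the plan definitely analyses T1 as an outcome, but the text does not say so. What survives is that no reading guarantees adjustment for T1.

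Four stronger inferences are tempting and are not supported:
- *The loss is worst for % body fat and PA.* This needs lower correlations for those outcomes than for BMI, and the documents give none. The 0.722 effect is also stated only for BMI.
- *Power could be 7% to 37%.* That range is for a group main effect averaged over T1-T4. The plan announces a comparison of changes, not that test.
- *Adjustment lifts power from 60% to 82%.* This sets a 3-df test against a 1-df contrast. With 3 df on both sides the move is 61% to 73% at r=0.5 and 61% to 60% at r=0.95.
- *The estimate is biased.* Allocation is random, so T1 imbalance is chance and adds noise without a systematic shift.

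It is also fair to say that the baseline t-tests do no direct harm, since nothing depends on them, and that 26 per arm assumes the full 20% loss although intention-to-treat analysis is also planned. The 32-per-arm column shows the same pattern without that loss.

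**Conclusion.** The point holds as a missing prespecification with a cost in precision. The plan should say that T1 is a covariate, and it does not. At 26 per arm the gain for a T4 contrast is about 12 power points at r=0.5, 4 to 5 at r=0.8 and 1 at r=0.95. For BMI, the outcome used for sample size, r is probably high and the gain probably small. These figures rest on the assumed correlations, equal variances at T1 and T4, and the plan's 0.722 applied to whichever outcome is considered.

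The shortfall in sample size is the larger power problem. It strengthens the case for using T1, because about 72% power leaves little to spare, but adjustment for T1 would not repair it at high r.

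For PA the governing analysis must be settled first. Section 13(d)(v) lists PA as an outcome and 13(d)(vii) covers continuous outcomes, while the accelerometer paragraph in 13(d)(vi) sends daily MVPA time to time-to-event and Cox models.

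**What to change.** In section 13(d)(vii):
1. State that the levels of time are T2, T3 and T4.
2. Include the same outcome's T1 value as a covariate in every continuous-outcome model, exempt from the p<0.1 rule.
3. Name the T1-adjusted group difference at T4, taken from the model with group, time and their interaction, as the tested contrast. Report it with its 95% CI.
4. Replace the pre-intervention t-tests with baseline means (SD) by arm.
5. For PA, reconcile the time-to-event text in 13(d)(vi) with 13(d)(v) and 13(d)(vii) before applying items 1 to 3.

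The cost is a few sentences. T1 is already scheduled for all participants in both arms, and no new data, staff or software are needed.
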